## **Statistical analysis**

Statistical analysis will be carried out using SPSS version 25.0. Descriptive Statistics for the categorical variables are performed by computing the frequencies (percentages) in each category. Comparison of categorical data between association of ABO and Lewis phenotypes in clinically confirmed CAD patients is done using chi-square test.

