## **Introduction**

Epidemiologic studies have found the Lewis negative phenotype to be independently associated with a two-fold higher prevalence of coronary artery disease and four-fold fatal coronary events . Lewis (a-b-) blood group has been reported to be associated with hypercholesterolemia, diabetes mellitus and insulin resistance conditions which eventually lead to CAD . Many studies have also shown the relationship between blood groups and different manifestations of cardiovascular disease .

Different clinical studies have shown that blood A phenotypes are more susceptible to coronary artery disease . The major one being the Framingham study .

In contrast, Garg P et al. reported a significant association between CAD and blood group B. while Sahita P et al. from Gujarat, India, did not observe any association between blood group and CAD. Cakir B et al reported a non- significant association between Lewis genotype and subclinical atherosclerosis and Saloma V et al. observed that carotid intima-media thickness was slightly higher among persons with Lewis negative phenotype than among persons with Lewis positive phenotype.

There is no literature from Kerala correlating Lewis antigen and ABO blood group with CAD, hence the present study to focus on the pattern and association of ABO and Lewis blood group phenotypes in clinically confirmed CAD patients.

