## **Rationale**

The present study aims to evaluate the association between Lewis antigen, ABO blood group, and coronary artery disease. This may allow identifying subjects at increased risk for coronary artery disease (CAD) and subsequently leading to more focused preventive measures and eventually to a specific treatment.

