### **Aim and Objectives:**

#### **Primary objective**

- To study the association of Lewis antigen and ABO blood group phenotypes with CAD patients attending the tertiary care hospital in Kerala.

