#### **Secondary objective**

- To find the association of Lewis antigen and ABO blood group phenotypes with smoking, alcohol use, diabetes, hypertension and dyslipidemia.

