### **Study design**

Hospital-based case-control analytical study

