## **Sampling:**

- Sample size**

Based on the proportion of Le(a-b-) observed in an earlier publication with 95% confidence level and 90% power, minimum sample size comes to 70 in cases and 140 in control group

$$n = \frac{[Z_{1-\alpha/2} \sqrt{2p(1-p)} + Z_{1-\beta} \sqrt{p_1(1-p_1) + p_2(1-p_2)}]^2}{(p_1 - p_2)^2}$$

- Inclusion criteria:**

- Patients in the age group of 30-55 years at the time of data collection
- Diagnosed with coronary artery disease on the basis of positive changes in coronary angiogram (More than 70% coronary stenosis)

- Exclusion Criteria:**

- Patients with other systemic illnesses like malignancy, autoimmune diseases.
- Patients who are not willing to participate in the study.

- Sampling procedure:**

First 70 cases attending the Cardiology department which satisfy the inclusion and exclusion criteria will be included in the study.

- Method of data collection**

70 cases attending the Cardiology department which satisfy the inclusion and exclusion criteria will be taken as cases. 140 age and gender matched healthy blood donors who are eligible to donate blood as per the inclusion and exclusion criteria of Drugs and Cosmetics Rules, 1945 are taken as controls.

After taking written, informed consent from the patients and blood donors satisfying the inclusion criteria, 3 mL blood is collected from cubital vein in Ethylene Diamine Tetra Acetic acid (EDTA) tubes under aseptic precautions. Samples are collected separately from each CAD patient as well as from blood donors.

Collection of blood samples repeatedly from the same subjects are avoided by personally verifying the subject's demographic profile such as full name, age, address, including hospital registration number and by collecting the blood sample in the required quantity.

Lipid profile values, fasting and post prandial blood sugar values will be collected from the laboratory information system. Blood pressure values will be obtained from the medical record and donor forms.

Diabetes mellitus is defined as fasting serum glucose  $>126$  mg/dL and or the reported use of diabetic medications. Hypertension is defined as systolic blood pressure (BP)  $>140$  or diastolic BP  $>90$  mmHg, or reported use of antihypertensive medications.

Alcohol use pattern is categorised as none, low/moderate use (1–14 drinks/week), and heavy use ( $>14$  drinks/week).

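### The analysis section plans only percentages and an unmatched chi-square for an age- and gender-matched case-control study, so the primary objective gets no effect estimate, no interval and no use of the matching

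*Combined protocol and SAP*

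**What the plan says.** The design is given as "Hospital-based case-control analytical study". The primary objective is "To study the association of Lewis antigen and ABO blood group phenotypes with CAD patients", so Lewis and ABO stand side by side in it.

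The Sampling section sets 70 cases and takes as controls "140 age and gender matched healthy blood donors who are eligible to donate blood". It does not say whether matching is individual or by frequency. The sample size is "Based on the proportion of Le(a-b-) observed in an earlier publication".

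The Statistical analysis section names SPSS 25.0, frequencies with percentages, and this: "Comparison of categorical data between association of ABO and Lewis phenotypes in clinically confirmed CAD patients is done using chi-square test". That is the whole analysis plan. A 95% confidence level appears only as an input to the sample size. No odds ratio, confidence interval, or regression, stratified or conditional analysis is mentioned anywhere.

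The proforma records age, sex and case/control status, but has no field for a matched set.

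**The concern.** Three things are missing for the primary objective.

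- **An estimate with its uncertainty.** The Rationale hopes to identify people at higher risk of CAD. A test result gives neither the size of an association nor its precision, and a non-significant Lewis result could be read as no association.
- **Use of the matching.** Age and gender shape who is recruited as a control and then play no part in the analysis. If matching is individual, the sets must be recorded during recruitment or they may be lost.
- **The ABO comparison.** A four-group chi-square does not show which group differs. The Review of literature cites findings for B, for A and non-O, and for A against the other groups. With no reference group or contrast named, one could be picked after the data are seen.

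**Working it through.** **The plan's own figure.** The only computed figure is 70 cases and 140 controls at 90% power. It cannot be reproduced, because the two Le(a-b-) proportions behind it are not given. The point does not depend on it.

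**Inputs.** The group sizes 70 and 140 come from the Sampling section. All phenotype counts below are assumed, because the documents give none.

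**Formulas.** For exposed and unexposed cases a, b and controls c, d: OR = ad/(bc), SE(log OR) = √(1/a + 1/b + 1/c + 1/d), and 95% CI = OR × exp(±1.96 SE). The test is the Pearson chi-square without continuity correction.

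**Step 1: Lewis, two assumed outcomes.**

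| Cases | Controls | Chi-square (1 df) | p | OR | SE | 95% CI |
|---|---|---|---|---|---|---|
| 28/70 (40%) | 28/140 (20%) | 9.55 | 0.002 | (28×112)/(42×28) = 2.67 | 0.323 | 1.42 to 5.02 |
| 19/70 (27%) | 28/140 (20%) | 1.37 | 0.24 | (19×112)/(51×28) = 1.49 | 0.342 | 0.76 to 2.91 |

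The second row is not significant, yet its interval contains 2.

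**Step 2: ABO.** Assume A/B/AB/O counts of 33/13/4/20 in cases and 38/38/8/56 in controls. The chi-square is 8.62 on 3 df, p = 0.035.

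- A vs O: (33×56)/(20×38) = 2.43 (1.22 to 4.86)
- B vs O: (13×56)/(20×38) = 0.96 (0.43 to 2.15)
- AB vs O: (4×56)/(20×8) = 1.40 (0.38 to 5.16)

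Swap A and B in the cases (13/33/4/20). The chi-square and p are unchanged, but A vs O becomes 0.96 and B vs O becomes 2.43. One test result fits opposite conclusions about A and B, so the test alone does not say which group differs.

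**Step 3: ignoring the matching.** Matching gives cases and controls the same age and gender mix. If the odds ratio within strata is constant, the crude odds ratio comes from the exposure proportions averaged over strata. Two sets of assumptions:

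- Within-set OR 2.67, 20% exposure in controls, normally distributed set-level log-odds: the crude OR is 2.67, 2.63 or 2.55 at a between-set SD of 0, 0.25 or 0.5.
- Stratum OR 2.5, four equal strata. Control exposure of 20% throughout gives crude 2.50. Exposure of 10, 15, 25 and 30% averages 20.0% in controls and 37.4% in cases, so crude OR = (0.374×0.800)/(0.200×0.626) = 2.39. Exposure of 5, 10, 30 and 50% averages 23.75% and 39.1%, giving 2.06.

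Wherever exposure varies between strata, the crude value moves towards 1. The shift is small unless phenotype frequency varies strongly with age or gender, and no section says that it does.

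**Step 4: error rates.** Simulating 70 against 140 with no association and the assumed control mix, the overall ABO test rejects in about 5% of runs, as it should. Now let only A differ (OR 2.43 to 4 against O), and read B vs O and AB vs O only after a significant overall test. At least one of these two intervals then wrongly excludes 1 in 6.6% to 7.1% of runs. Reading contrasts after the overall test is therefore not full error control.

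**The case against.** The strongest reply is that the plan already meets its objective. The objective is association, and a chi-square tests association validly. The percentages will be reported with known group sizes, so anyone can compute a crude odds ratio and its interval. The Rationale is motivation and sets no estimation target. Ignoring the matching costs little in most illustrations and, because it moves the estimate towards 1, shows no false-positive risk. All of this stands, and it limits the weight of the point. It does not remove it: a matched or age- and sex-adjusted odds ratio cannot be recovered from published percentages, and the ABO reference group would still be open.

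A reader might infer three stronger charges, which the documents do not support.

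- **That the plan has an ABO false-positive rate of 12% to 13%.** That rate arises if four unadjusted contrasts (A, B, AB and non-O, each against O) are all read. The plan contains none of them. Read as one overall ABO test, it has a rate of about 5%.
- **That the controls are left out of the analysis.** The test sentence names only CAD patients, but it echoes the Introduction's description of the topic, "the pattern and association of ABO and Lewis blood group phenotypes in clinically confirmed CAD patients". The design, objective and sampling sections make the case-control comparison clear. This is a matter of wording.
- **That ABO is really a secondary question.** Le(a-b-) is the basis of the sample size only. The primary objective names both systems.

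**Conclusion.** The point holds as an omission that should be fixed. For a matched case-control study, the plan gives no effect estimate or interval for either part of the primary objective, does not use the matching, and leaves the ABO comparison unspecified beyond a test that cannot say which group differs. The omission itself is read directly from the text and rests on no assumption.

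Its numerical consequences rest on assumed phenotype counts. They show that a non-significant Lewis result can leave an odds ratio of 2 open, and that one ABO p-value can fit opposite group effects. The bias from ignoring the matching is towards 1 and probably small. In the illustrations it runs from none to 2.50 falling to 2.06, and the documents cannot settle where this study lies. The planned chi-square is limited as the sole analysis, but it is not invalid. The conclusion concerns the primary objective only.

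**What to change.** Amend the Statistical analysis section along these lines:

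- For both parts of the primary objective, compare the 70 cases with the 140 controls using odds ratios and 95% CIs.
- Lewis: Le(a-b-) against the other Lewis phenotypes, the basis of the sample size.
- ABO: O as the reference group, with A, B and AB each compared with O. Keep the overall ABO test as the test of association. Report all three contrasts as descriptive estimates whatever its result, and do not claim that reading them after the overall test fully controls error.
- State the type of matching. If by frequency, use logistic regression adjusted for age and sex, both already on the proforma. If individual, use conditional logistic regression on the matched sets and add a set number to the proforma.
- Leave ABO in the primary objective.

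The cost is a few sentences and, only if matching is individual, one proforma field. No extra participants or laboratory tests are needed. The AB interval will be wide (0.38 to 5.16 in the illustration), and the report should say so.

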## **Estimated expenditure**

Establishment

- Antisera : ₹ 50000/-
- Vacutainers : ₹ 1700/-

Equipment

: nil

Research literature

: ₹ 1000

Cost of preparation of research papers : ₹ 1000

Expenditure will be met by the institution.

## **Ethical Considerations**

No ethical issues expected. Study will be conducted only after the approval of the ethical committee.

**PROFORMA****CASE****CONTROL**

Name : \_\_\_\_\_

Age: \_\_\_\_\_

Sex: \_\_\_\_\_

Hosp Number: \_\_\_\_\_

Address : \_\_\_\_\_

\_\_\_\_\_

Presenting complaints : \_\_\_\_\_

Past history : \_\_\_\_\_

Personal history : \_\_\_\_\_

Tobacco use  \_\_\_\_\_Alcohol  \_\_\_\_\_**Physical Examination**

Height: \_\_\_\_\_ Kg

Weight: \_\_\_\_\_ cm

BMI: \_\_\_\_\_

**Investigations**

Angiogram : \_\_\_\_\_

Hypertension:  yes  noOn medication:  yes  no

BP: \_\_\_\_\_ mmHg

Lipid profile:

Total Cholesterol : \_\_\_\_\_ mg/dL

TG : \_\_\_\_\_ mg/dL

HDL : \_\_\_\_\_ mg/dL

LDL : \_\_\_\_\_ mg/dL

Diabetes:  yes  noOn medication  yes  no

PPBS : \_\_\_\_\_ mg/dL

FBS : \_\_\_\_\_ mg/dL

Blood Group			
A	B	AB	O
+	-		

Rh	
+	-

Le a	
+	-

Le b	
+	-
